Procedures: N=40 parent/child dyads will receive a weekly monetary incentive for losing weight during an initial 12 week weight-loss program. During this time, half of the families will receive EFT training (N=20) and the other half will receive a control thought training program (N=20). After 12 weeks, the monetary incentives program will be terminated, but the parent/child dyads will continue their respective EFT or control thought training programs for an additional 12 weeks. At the end of the additional 12 weeks, weight-loss maintenance will be examined between dyads that received EFT and dyads that received control thought training.

Procedures Cohort 2:

Procedures: N=20 parent/child dyads will receive a weekly monetary incentive for losing weight during an initial 8 week weight-loss program. During this time, half of the families will receive EFT training (N=10) and the other half will receive a control thought training program (N=10). After 8 weeks, the monetary incentives program will be terminated, but the parent/child dyads will continue their respective EFT or control thought training programs for an additional 8 weeks. There will then be an 8 week no intervention follow-up period. At the end of the follow-up period, weight-loss maintenance will be examined between dyads that received EFT and dyads that received control thought training.

Purpose (Cohort 3): To assess whether episodic future thinking (EFT), thought training that teaches individuals to think prospectively about future events as if they were happening now, promotes healthier grocery shopping behaviors in parent and child dyads in which the child is obese/overweight, and to assess subsequent weight loss.

Procedures Cohort 3:

N=6-12 parent/child dyads will receive the full family-based therapy program with a specialized EFT component focused on grocery shopping during this 15 week weight-loss program. This study is a nonconcurrent multiple baseline design; participants will be randomized to a 4 week, 7 week, or 10 week group with staggered baseline periods followed by 4-8 weeks of the intervention consisting of FBT and EFT.

1.4 Specify your research question(s), study aims or hypotheses: We hypothesize that:

1) Parent/child dyads in both the EFT and the CONTROL thought training conditions will lose weight with the monetary incentive program.

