Session 2- Baseline: ~ 1 Hour 30 Minutes:

During the baseline session, participants will complete the following:

1- Surveys: Consideration of Future Consequences Scale (CFCS), Palatable Eating Motives Scale (PEMS), and Living to 75 assessment.

2- Delay Discounting Task

- 3- Relative Reinforcing Value Task (will assess level of hunger before the task- hunger scale attached).
- 4- EFT or CONTROL cue generation needed for thought training.

EFT Cues: A brief cue will be generated in which participants talk about a specific future positive event where they imagine themselves in vivid detail. To generate the cues, participants in the EFT group will be given standardized instructions asking them to think about and list specific events that they are looking forward to in the future (ex: parties, holidays, etc.). Participants will be instructed to generate the EFT cue by describing their events, including a detailed description of themselves at the specific event. After the cue is created, participants will rate this cue for valence, salience, arousal, and the frequency and vividness of episodic associations. Participants who do not rate the cue at least 3 out of 5 for vividness will be asked to generate a new cue using a different event. After the participant has created their cues, they will save their cue for later use in the intervention.

Control Cues: To control for the timing and attention of the EFT cue, participants in the CONTROL group will generate cues that include a specific nutrition statements, selecting cues that they feel will be of personal benefit. To generate the cues, participants in the CONTROL group will select from a list of nutrition statements that they feel will be personally useful in making healthy decisions. After the cue is created, participants will rate this cue for salience. After the participant has created their cues, the participant will save their cue for later use in the intervention.

5- Technology Tutorial: Participants will be learning to use 3 major technologies for this study including:

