If the parent or child fails to meet his/her weekly weight-loss goal, the potential earning potential of the participant drops back down to the amount of Session 3 (\$0.50). The earning potential will go back up to the expected pay rate after 2 weeks of successive losses. For example, if during the week of Session 6, a parent does not meet his/her weight-loss goal, he/she will not receive a monetary incentive for the week and the earning potential of the week of Session 7 will drop down to \$0.50. If the parent meets his/her weight loss goal during the week of Session 7 and the week of Session 8, the earning potential will be back at \$5.00.

If both the parent and child meet their weight-loss goals (parent loses 1 lb and child loses 1/2 lb), the parent/child dyad will receive the amount below in addition to the separate parent/child incentive amount. The amount will be split evenly between the parent and child each session.

Session 3 \$4.20 (or \$2.10 each) Session 4 \$4.20 Session 5 \$4.20 Session 6 \$4.20 Session 7 \$4.20 Session 7 \$4.20 Session 9 \$4.20 Session 10 \$4.20 Session 11 \$4.20 Session 12 \$4.20 Session 13 \$4.20 Session 14 \$4.20

Families will also receive \$20 in compensation for measurement sessions (sessions 2, 7, 10, 14, 18, 26). The \$20 will be split evenly between parent and child (\$10 each).

Sessions 3-6 ~ 1 Hour 30 Minutes Each

In-Lab Group Sessions: One researcher will lead a session for the parents and one researcher will lead a session for the children. During these sessions, families will be given information about the Traffic Light Eating Plan which lays out healthy vs. unhealthy foods, reducing serving sizes, eating less, recording their diets, shopping, meal planning, and keeping up healthy behaviors. Participants will have their heights (session 3), weights, and waist circumferences measured during the session. Families will also have a short case management session with the researcher during this session so the researcher can help them best succeed in the Healthy Habits Program.

Session 7 ~ 1 Hour

In-Lab Individual Family Session: Each family will come to the lab for measurements, case management, and payment. Height, weight, waist circumference, and DD will be measured during this session. Participants will also generate new EFT or CONTROL cues.

Sessions 8-9 ~ 20 Minutes Each

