 - Procedures include a confederate pretending to be another participant in the study.
 - Participants will be told that the research includes completion of a particular task, when in fact, that task will not be administered.
 - Study is designed to introduce a new procedure (or task) that participants are not initially told about.

No

- **1.18** Indicate any payments or reimbursements to participants (check all that apply)
 - CashGift or Debit Card
- 1.19 Does this study have a plan to have an individual or committee review combined data from all participants on a periodic basis (such as summary or aggregate safety and/or efficacy data)? No
- **1.20** What have you done to minimize any risks?
 - No foreseeable risks
 - Psychological consultation and/or referrals readily available
 - **1.21** What are the potential benefits related to this project for:
 - the participant (if any)
 - benefits to society (if any)

There are many potential benefits of the proposed research. Participants in the study could gain new knowledge on how episodic future thinking influences inter-temporal decision making. All participants in all groups are taught methods for healthier grocery shopping, eating and living; therefore, depending on the behavior changes of the participants, it could result in a healthier eating behaviors and a healthier home environment. This in turn could result in potential weight loss for the entire family in the home. If participants do lose weight in the study, it could decrease their risk of weight-related disease such as type 2 diabetes and heart disease.

1.22 Provide a summary of the analysis methods you will use, including, if applicable, the data points or outcomes you will analyze.

Cohort 1:

Preliminary analyses:

Preliminary analyses will be conducted to ensure groups are similar based on demographic characteristics (age, BMI, race/ethnicity, SES).

Primary analyses:

Between group ANOVAs will be performed to make sure the two groups have similar continuous characteristics (age, BMI for adults/percent over BMI for children) and chi-square analyses will be performed to ensure the groups have similar categorical characteristics (race/ethnicity, SES). If a group difference is found, the variable will be entered as a covariate in subsequent analyses.

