Two-way repeated measures ANOVAs will then be conducted to determine differences in BMI/percent over BMI, weight, and waist circumference, between the EFT and HT groups over time. Data points will be collected at weeks 2 (baseline), 7, 10, 14 (incentive program ends), 18, and 26 of the program. We hypothesize:

1- The EFT and HT group will both have a reduction in BMI/percent over BMI, weight, and waist circumference from baseline throughout the monetary incentives program (week 7, 10, 14).

2- The EFT group will have a greater reduction in BMI/percent over BMI, weight, and waist circumference from baseline throughout the monetary incentives program (week 7, 10, 14) than the HT group.

3- The EFT group will maintain the reduction in BMI/percent over BMI, weight, and waist circumference from baseline after the termination of the monetary incentives program (week 18, 26).

4- The HT group will not maintain the reduction in BMI/percent over BMI, weight, and waist circumference from baseline after the termination of the monetary incentives program (week 18, 26).

Secondary analyses:

A two-way repeated measures ANOVA will be conducted to determine differences in delay discounting between the EFT and HT groups over time. Data points will be collected at weeks 2 (baseline), 7, 10, 14 (incentive program ends), 18, and 26 of the program. We hypothesize:

- 1- The EFT group will have a reduction in delay discounting over time (7, 10, 14, 18, 26) compared to baseline.
- 2- The HT group will not have a reduction in delay discounting over time (7, 10, 14, 18, 26) compared to baseline.

3- The EFT vs. the HT group will have a reduction in delay discounting over time (7, 10, 14, 18, 26).

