Secondary analyses: A two-way repeated measures ANOVA will be conducted to determine differences in delay discounting between the EFT and HT groups over time. Data points will be collected at sessions 2 (baseline), 11 (incentive program ends), 19, and 20. We hypothesize:

1- The EFT group will have a reduction in delay discounting over time (11, 19, 20) compared to baseline.

2- The HT group will not have a reduction in delay discounting over time (11, 19, 20) compared to baseline.

3- The EFT vs. the HT group will have a reduction in delay discounting over time (11, 19, 20).

Regression analyses will also be conducted to determine whether baseline characteristics predict outcome variables (BMI for adults/percent over BMI for children, weight, and DD). These characteristics will be collected from baseline surveys including the Consideration of Future Consequences Scale, Living to 75 Assessment, and Palatable Eating Motives Scale. First, zero order correlations between each predictor and the outcome variables will be established, and then significant predictors will be entered in a multiple regression model that includes demographic characteristics predict child and adult success. In addition, we will assess the influence of parental success on child success in a multiple regression model, again controlling for demographic characteristics.

The results of this study will be analyzed graphically as well as assessing the degree of change from baseline to treatment across the three replications.

1.23 Provide the rationale or power analysis to support the number of participants proposed to complete this study. This is the first study of this kind, therefore, we were unable to conduct a power analysis. Additionally, a power analysis is not applicable to this multiple baseline design. We are collecting weekly data from participants and will have enough data points to ensure we will be able to achieve the study objectives. The results of this study will be analyzed graphically as well as assessing the degree of change from baseline to treatment across the three replications. For an example of a study that utilized a multiple baseline design, see:

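### The between-arm delay-discounting hypothesis has no named contrast and leaves the collected baseline unused as a covariate; a prespecified baseline-adjusted comparison alongside the ANOVA would gain power if the effect is sustained

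*Combined protocol and SAP*

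**What the plan says.** Section 1.22 gives the same sentence for the secondary analysis in Cohorts 1 and 2: "A two-way repeated measures ANOVA will be conducted to determine differences in delay discounting between the EFT and HT groups over time". HT is the control thought-training arm.

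- **Cohort 1 time levels.** "Data points will be collected at weeks 2 (baseline), 7, 10, 14 (incentive program ends), 18, and 26 of the program". That is six levels, baseline included. The week numbers match the session numbers in section 1.13.
- **Cohort 2 time levels.** Four: a baseline, then sessions 11, 19 and 20.
- **Hypothesis 3.** Cohort 1: "The EFT vs. the HT group will have a reduction in delay discounting over time (7, 10, 14, 18, 26"). Cohort 2: "The EFT vs. the HT group will have a reduction in delay discounting over time (11, 19, 20"). Neither names a contrast, a visit or a model term.
- **Covariates.** "If a group difference is found, the variable will be entered as a covariate in subsequent analyses". The variables screened are age, BMI or percent over BMI, race/ethnicity and SES. Baseline delay discounting is not among them.
- **Collection.** In Cohort 1 the baseline session lists "2- Delay Discounting Task" ahead of cue generation, and sessions 7, 10, 14, 18 and 26 each state: "Height, weight, waist circumference, and DD will be measured during this session". In Cohort 2, section 1.13 also puts the task ahead of cue generation, at session 3. The delay-discounting paragraph of section 1.22 calls session 2 the baseline instead.
- **Power.** Section 1.23 says that no power analysis could be done.

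**The concern.** Hypothesis 3 is directional: lower discounting under EFT than under control after training. A two-way repeated measures ANOVA yields an arm main effect and an arm-by-time interaction, and the plan does not say which one answers the hypothesis.

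The interaction has 5 df in Cohort 1 and 3 df in Cohort 2. It responds to any difference in profile, so a significant result would not by itself show that EFT is lower. The arm main effect averages in a baseline visit at which no difference is expected. In both, baseline is an outcome level, so its correlation with later values is not used as efficiently as a covariate would use it.

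Reduced discounting is the mechanism on which section 1.5 rests the case for EFT. With 20 or 10 dyads per arm, a loosely specified and inefficient test could easily be read as no effect on the mechanism, and an unnamed contrast leaves room to choose one after seeing the data.

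**Working it through.** **Inputs from the documents.** Cohort 1: "half of the families will receive EFT training (N=20) and the other half will receive a control thought training program (N=20"), so n = 20 per arm, with p = 5 post-baseline visits. Cohort 2: n = 10 per arm (section 1.3), p = 3.

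**Assumed, because the documents give none of it.** Two-sided alpha 0.05; complete data; equal variances; the same correlation r between any two visits (compound symmetry), r = 0.5 to 0.7; no arm difference at baseline and a constant difference of d SD afterwards; parents or children analysed one set at a time. The plan states no power figure to reproduce.

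**Formulas** (noncentral F with noncentrality λ):

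1. Interaction: λ = (n/2)·d²·[p/(p+1)]/(1−r); df p and p(2n−2).
2. Unadjusted change (post-baseline mean minus baseline): same λ; df 1 and 2n−2.
3. Baseline-adjusted post-baseline mean: residual variance v = (1−r)(1+pr)/p; λ = (n/2)·d²/v·[1−1/(2n−2)]; df 1 and 2n−3.

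**Cohort 1, d = 0.5.**

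- Tests 1 and 2: λ = 10 × 0.25 × (5/6)/0.5 = 4.167 at r = 0.5, and 6.944 at r = 0.7.
- Test 3: v = 0.5 × 3.5/5 = 0.35 at r = 0.5, so λ = (2.5/0.35) × (37/38) = 6.955. At r = 0.7, v = 0.3 × 4.5/5 = 0.27 and λ = 9.016.

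| Case | r | Interaction | Unadjusted change, 1 df | Adjusted mean, 1 df |
|---|---|---|---|---|
| Cohort 1, 0.5 SD | 0.5 | 0.295 | 0.512 | 0.729 |
| | 0.6 | 0.367 | 0.604 | 0.766 |
| | 0.7 | 0.484 | 0.728 | 0.832 |
| Cohort 2, 0.5 SD | 0.5 | 0.172 | 0.254 | 0.355 |
| | 0.7 | 0.267 | 0.387 | 0.453 |
| Cohort 2, 0.7 SD | 0.5 | 0.310 | 0.442 | 0.603 |
| | 0.7 | 0.495 | 0.649 | 0.731 |

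**Where the gain comes from.** Going from column 3 to column 4 is the move to one degree of freedom. Going from column 4 to column 5 is the baseline adjustment: the variance ratio of test 3 to test 2 is (1+pr)/(p+1), which in Cohort 1 is 3.5/6 = 0.58 at r = 0.5 and 4.5/6 = 0.75 at r = 0.7.

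**If the arm main effect is the tested term.** Cohort 1, 0.5 SD: power 0.390 (r = 0.5) and 0.317 (r = 0.7), below the adjusted mean.

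**Range.** For sustained effects of 0.3 to 0.8 SD and r of 0.3 to 0.8 in Cohort 1, the power of the adjusted mean is 1.0 to 3.6 times that of the interaction. It is near 1 where both tests are already strong.

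**Other effect shapes.** The interaction λ becomes (n/2)·Σ(δₜ−δ̄)²/(1−r), summing over all visits including baseline (δ = 0 there); the adjusted contrast uses the mean of the post-baseline δₜ.

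| Shape | Interaction, r 0.5-0.7 | Adjusted mean, r 0.5-0.7 |
|---|---|---|
| Cohort 1: 0.2, 0.3, 0.4, 0.5, 0.6 (4,000 simulations) | 0.336-0.544 | 0.524-0.647 |
| Cohort 1: 0.6, 0.6, 0.6, 0.4, 0.2 (4,000 simulations) | 0.445-0.704 | 0.684-0.802 |
| Cohort 1: 0.5 to session 14, then 0 | 0.519-0.774 | 0.338-0.419 |
| Cohort 1: 0, 0, 0.2, 0.5, 0.8 | 0.716-0.926 | 0.338-0.419 |
| Cohort 2: 0.7, 0.7, then 0 at session 20 | 0.405-0.629 | 0.317-0.405 |

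Gradual building or partial fading still favours the adjusted mean. An effect that is lost entirely, or that appears only late, reverses the ranking.

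**Correlation that decays with time (Cohort 1, simulated).** The uncorrected interaction F has type I error of about 0.075 to 0.08. With the Greenhouse-Geisser correction and a constant 0.5 SD, power is 0.202 against 0.602 for the adjusted mean (adjacent-visit correlation about 0.7), and 0.344 against 0.710 (about 0.85).

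**The case against.** Section 1.22 is a summary on an ethics-board form and never says that the interaction is the tested term. That stands. A reader might infer that the plan commits to a 5-df test and that the adjusted contrast roughly doubles its power. The documents support neither. The interaction is the natural reading, but the term is unnamed. Against a one-df change contrast taken from the same ANOVA, the Cohort 1 gain at 0.5 SD is only about 1.1 to 1.4 times (0.832/0.728 and 0.729/0.512). A doubling needs the interaction as comparator, a moderate constant effect and mid-range correlation.

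A reader might also infer that the ANOVA should be reduced to description. That does not follow. Incentives stop at session 14 in Cohort 1, and session 20 in Cohort 2 follows eight weeks without intervention, so an effect that vanishes is plausible, and there the interaction has more power. The trial's main question also concerns what happens after incentives end, and a plain average mixes visits before and after that point.

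Two limits remain. In Cohort 2 at 0.5 SD the adjusted contrast still reaches only 36-45%, so it would miss the effect more often than not. And delay discounting is a secondary outcome in both cohorts. None of this is a reason to leave the contrast unnamed or baseline unused: adjusting for baseline beats the same contrast unadjusted in every case computed.

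**Conclusion.** The point holds as a specification gap with a cheap gain in efficiency. Hypothesis 3 has no named between-arm contrast, baseline is a level of the time factor, and the collected baseline value is not a covariate.

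The firmest part of the gain is baseline adjustment: in Cohort 1 at 0.5 SD, from 51-73% to 73-83%. The larger comparison, from 29-48%, applies only if the interaction is the test. Both rest on the assumptions listed above, none of which the documents supply, and the comparison with the interaction also depends on the effect being sustained. The averaged contrast should therefore answer hypothesis 3 while the arm-by-time analysis stays in the report. This is worth changing, but it does not threaten the primary weight analyses.

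**What to change.** In section 1.22, for hypothesis 3 in each cohort:

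1. Prespecify one comparison: regress the mean post-baseline delay discounting (Cohort 1: 7, 10, 14, 18, 26; Cohort 2: 11, 19, 20) on arm and baseline delay discounting, separately for parents and children. The arm coefficient, with its confidence interval, answers hypothesis 3.
2. Keep the arm-by-time ANOVA as a reported analysis of how the difference changes over visits. Name its tested term and the sphericity correction, and plot the visit means.
3. Say how the mean is formed when a visit is missed; the power figures assume none are.
4. For Cohort 2, reconcile the baseline session first: section 1.22 says session 2 for delay discounting, section 1.13 places the task at session 3. Confirm that the value used precedes cue generation.

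The cost is a few lines of text and no new data. The price is lower power from the averaged contrast if the effect comes late or disappears (for example 32-41% against 41-63% in Cohort 2 if 0.7 SD is lost by session 20), which is why the ANOVA stays.

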Regression analyses will also be conducted to determine whether baseline characteristics predict outcome variables (BMI for adults/percent over BMI for children, weight, waist circumference, and DD). These characteristics will be collected from baseline surveys including the Consideration of Future Consequences Scale, Living to 75 Assessment, and Palatable Eating Motives Scale. First, zero order correlations between each predictor and the outcome variables will be established, and then significant predictors will be entered in a multiple regression model that includes demographic characteristics and the significant predictors. This will provide the opportunity to assess what individual characteristics predict child and adult success. In addition, we will assess the influence of parental success on child success in a multiple regression model, again controlling for demographic characteristics.

Cohort 2:

Preliminary analyses will be conducted to ensure groups are similar based on demographic characteristics (age, BMI, race/ethnicity, SES).

Primary analyses: Between group ANOVAs will be performed to make sure the two groups have similar continuous characteristics (age, BMI for adults/percent over BMI for children) and chi-square analyses will be performed to ensure the groups have similar categorical characteristics (race/ethnicity, SES). If a group difference is found, the variable will be entered as a covariate in subsequent analyses.

Two-way repeated measures ANOVAs will then be conducted to determine differences in BMI/percent over BMI and weight between the EFT and HT groups over time. Data points will be collected at sessions 3 (baseline), 11 (monetary incentives end), 19, 20. We hypothesize:

1- The EFT and HT group will both have a reduction in BMI/percent over BMI and weight, and waist circumference from baseline throughout the monetary incentives program (session 11).

2- The EFT group will have a greater reduction in BMI/percent over BMI and weight throughout the monetary incentives program (session 11) than the HT group.

3- The EFT group will maintain the reduction in BMI/percent over BMI and weight from baseline after the termination of the monetary incentives program (session 19, 20).

4- The HT group will not maintain the reduction in BMI/percent over BMI and weight from baseline after the termination of the monetary incentives program (session 19, 20).

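### Baseline survey scales are screened and then tested on the same 40 or 20 dyads, so p-values and effect sizes for the scales that enter the regression are not valid as reported

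*Combined protocol and SAP*

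**What the plan says.** Under the Cohort 1 secondary analyses, section 1.22 plans regressions of the outcomes ("BMI for adults/percent over BMI for children, weight, waist circumference, and DD") on baseline survey measures that include the "Consideration of Future Consequences Scale, Living to 75 Assessment, and Palatable Eating Motives Scale". The rule has two steps. "First, zero order correlations between each predictor and the outcome variables will be established", "then significant predictors will be entered in a multiple regression model that includes demographic characteristics and the significant predictors". Demographics enter without a screen. The stated purpose is to learn which individual characteristics predict success in children and in adults.

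Cohort 2 repeats the rule with three outcomes (waist circumference is dropped), but the sentence is garbled: "significant predictors will be entered in a multiple regression model that includes demographic characteristics predict child and adult success".

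Section 1.3 gives the sizes: "N=40 parent/child dyads will receive a weekly monetary incentive for losing weight during an initial 12 week weight-loss program" (Cohort 1) and "N=20 parent/child dyads will receive a weekly monetary incentive for losing weight during an initial 8 week weight-loss program" (Cohort 2). Section 1.22 states no alpha, outcome time point, multiplicity adjustment, hold-out sample or cross-validation for this step, and does not call the results exploratory. Section 1.23 reports that no power analysis was done.

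**The concern.** A scale reaches the final model because its correlation with the outcome was large in these data. The model then tests it in the same data as if it had been chosen in advance. Its p-value takes no account of that selection, and its coefficient has been picked for being large. The scales that enter are also the ones that will be reported and interpreted.

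The screen can err in the other direction too. It looks at the marginal correlation, so a scale whose relation to the outcome is hidden by variation due to a demographic variable may be dropped before the model that would have shown it.

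At stake is the plan's answer to which characteristics predict success. In samples this small, a reader could take a selected and inflated association for an established one.

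**Working it through.** The plan gives no figure to reproduce for this analysis, so the two-step rule was simulated with scales that have no relation to any outcome.

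**Inputs from the documents.** 40 and 20 dyads (section 1.3); at least three scales; four outcomes in Cohort 1 and three in Cohort 2; two generations (section 1.22). The balance check in section 1.22 lists four demographic characteristics: age, BMI, race/ethnicity and SES.

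**Assumptions.** Two-sided alpha 0.05 at both steps; one score per scale; the four demographics give 4 to 6 model terms; scales correlated 0 or 0.3; outcomes correlated 0.7; no dropout. There were 4,000 to 6,000 simulated trials per setting.

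**Step 1: what passes the screen.** The critical correlation is r = t/√(n − 2 + t²).
- n = 40: t = 2.024, so r = 2.024/√(38 + 4.098) = 0.312.
- n = 20: t = 2.101, so r = 2.101/√(18 + 4.414) = 0.444.

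The true correlation of a noise scale is zero, yet those that pass average |r| of about 0.37 and 0.52.

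**Step 2: the final test.** The prognostic rows give one demographic term a coefficient of 0.7.

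| Noise scale | n = 40 | n = 20 |
|---|---|---|
| Passes the screen | about 5% | about 5% |
| Final p < 0.05 once in, demographics unrelated to outcome | 57-69% | 41-54% |
| Same, one demographic prognostic | 39% | 34% |
| Passes both steps, demographics unrelated | 2.7-3.5% | 2.1-2.8% |
| Same, one demographic prognostic | 1.9% | 1.7% |
| p < 0.05 with all three scales entered, no screen | 4.8-5.0% | 4.9-5.2% |

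The rows agree with each other: at n = 40, 0.05 × 0.69 = 0.035 and 0.05 × 0.39 = 0.019. Other assumed outcome correlations and demographic effects widen the conditional figure to about 35-70% at n = 40 and 30-57% at n = 20. With a very strong demographic effect (2 SD) it falls to 14% and 12%, still above 5%.

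**Step 3: real predictors.** For a true coefficient of 0.40, estimates that survive the screen average 0.50 at n = 40 and 0.59 at n = 20. At n = 40 with a strongly prognostic demographic, power is 23% with the screen and 59% without it. The loss shrinks as the demographics become less prognostic.

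**Step 4: number of tests.**
- Cohort 1: 3 × 4 × 2 = 24 screens; 24 × 0.05 = 1.2 false passes expected; 1 − 0.95²⁴ = 71% chance of at least one if independent.
- Cohort 2: 3 × 3 × 2 = 18 screens; 18 × 0.05 = 0.9 expected; 1 − 0.95¹⁸ = 60%.

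Allowing for correlated outcomes, at least one false predictor survives both steps per generation in Cohort 1 (12 tests) in 22-26% of trials, or 15% with a prognostic demographic. It is 32% if only three of the four outcomes are correlated, at 0.6. Without the screen and without adjustment, the 22-26% becomes 32-34%, and the 32% becomes 42%. Bonferroni over the 12 unscreened tests (0.05/12 = 0.0042) brings the rate to 3.5-4.2%.

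**The case against.** The strongest objection is that the screen protects rather than harms. A given noise scale gets through both steps less than 5% of the time, and removing the screen without adjustment raises the chance of some false positive. That stands. A reader might infer that the screen inflates the false-positive rate, or that noise is bound to be reported as a predictor; the calculations support neither. The fault is conditional: it lies in the p-values and coefficients of the scales that enter.

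Second, the upper figures assume demographics unrelated to the outcome. BMI is listed as a demographic and is also an outcome, so this may be unrealistic if outcomes are analysed as levels. That stands too, and is why a range is given.

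Third, the model as described does not name study arm, and a reader might infer bias. The documents do not support this. Arm is randomised, so it is unrelated to the baseline scales in expectation, and the wording does not exclude it. Leaving it out costs precision.

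Finally, this is a secondary analysis in a form that asks only for a summary of methods. That limits the weight of the point, but the two-step rule is stated explicitly and would be followed as written.

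**Conclusion.** The point holds in this limited form. Under the stated rule, p-values are not valid and effects are inflated for the baseline survey scales that enter the model: for a noise scale that passes, roughly 35-70% final significance at n = 40 and 30-57% at n = 20, where 5% is nominal. Real predictors can also be lost at the screen. The 15-32% chance per generation in Cohort 1 of some spurious predictor is mainly a multiplicity problem, which dropping the screen alone would not cure.

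The sizes rest on an assumed alpha of 0.05, one score per scale, 4 to 6 demographic terms and assumed correlations. Subscales or several time points would add tests. A reader might extend the concern to the trial's main conclusion, but the EFT versus control comparisons are separate repeated measures analyses and do not use this screen. The change should be made; the main result does not depend on it.

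**What to change.** In section 1.22, for both cohorts:

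- Remove the screening step. For each outcome, at one named time point, fit one prespecified model per generation with the three scales, study arm, the baseline value of the outcome and the demographics. Arm and baseline are there for precision. Where the baseline value is already among the demographics (BMI), enter it once.
- Name the score used from each scale and state alpha.
- Report all estimates with confidence intervals. Either adjust for multiplicity across scales and outcomes or make no significance claims. Label the results exploratory.
- For Cohort 2, use a short prespecified covariate list. Three scales, arm, baseline and 4 to 6 demographic terms make 9 to 11 terms; with the intercept, 20 − 10 = 10 to 20 − 12 = 8 residual degrees of freedom remain.
- Repair the broken Cohort 2 sentence.

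This is a change of wording and needs no new data. The price is wider intervals, especially in Cohort 2. If multiplicity is left unadjusted, more scales, not fewer, will be nominally significant when nothing is there.
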